10.3 Access to Source Data and Documentation

The PI should guarantee access to source documents for the monitor and auditors as well as for inspection by appropriate regulatory agencies, and the IEC, if required.

11.1 Statistical design, method and analytical procedures

Statistical analysis on variables of interest, including subject demographics, baseline characteristics, effectiveness and safety endpoints will be summarized descriptively by randomization arm. Students 't' Test for comparative testing, will address testing the hypothesis statements, along with p values reported for significance. Mean, standard deviation, range, and Coefficient of Variation (CV) will be reported for closure times for both the two closure treatment methods of SoC suture and Zip 4 device for the primary endpoint.

For the secondary endpoints, mean, standard deviation, range, and CV will be provided for the VAS scale data, plus comparative "t" test will be applied for testing any possible significant differences between the two treatment groups. Additional analysis will be reported per the attribute satisfaction survey criteria obtained from patient satisfaction data at the 30 day follow-up interval. This will include an analysis of Average Satisfaction Scores, summary statistics, plus a histogram analysis comparing patient satisfaction data for both treatment groups of Sutures and Zipline.

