8.3 Hypothesis

The hypothesis for the primary endpoint is:

H₀: Mean time for Zip 4 device wound closure procedure = Mean time for standard of care sutures wound closure procedure

H₁: Mean time for Zip 4 device wound closure procedure \neq Mean time for standard of care sutures wound closure procedure

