9.6.3 Number of Subjects

The study population will be comprised of 60 pediatric patients presented to the Pediatric energency department with need of laceration repair, and eligible to study participation according to the inclusion and exclusion criteria. The subjects will be randomly assigned at a 1:1 ratio to either the Zip 4 group (30 subjects) or to the SoC group (30 subjects).

The sample size calculation was based on preliminary data indicating a difference of approximately 30 minutes in wound treatment procedures between the Zip device and SoC sutures. Alpha = 0.05 and power of the test = .9, indicates a sample size of 24 subjects. Assuming 10% dropout rate, the study will include up to 26 subjects. If for any reason the dropout rate should be higher than this, additional subjects might be enrolled in the study to reach a total of 24 completed subjects. Since different areas of the body are being appreciated we will enroll 60 patients.

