- Follow up visits will be scheduled and the subject and their legal representative(s) will be reminded of the importance of attending. These will be done either at the subjects home or at the Pediatric Emergency Department at Kaplan Medical Center.

During Visit 1 the following assessments/procedures will be performed:

- Demographics
- Relevant medical and surgical history
- Physical examination of the laceration (type, size, location)
- Medication review
- Verification of subject eligibility (check inclusion/exclusion criteria)
- Randomization
- Wound preparation, e.g. cleansing.
- Anesthesia (if required)
- Sedation (if required)
- Photographs taken at the wound prior device application
- Device application
- Dressing application
- VAS
- Study participant instructions: hand out Zip device removal instructions and photograph instructions

- Hand out questionnaires (VAS and Wound healing satisfaction questionnaire) and selfaddressed envelopes to be filled out in conjunction with the telephone follow up 1 and 2.
- Telephone follow ups scheduled

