11.2 Sample size

Sample sizes for the two treatment groups of Zip 4 device and SoC suture, were determined, and based on prior studies performed for the primary endpoint of mean times for incision closure time. The justification for sample sizes determined, is based on the following delta differences, and pooled Standard Deviation (SD) calculations for mean time differences of closure methods.

Differences and variances are based on prior data, with a delta difference of 30 mins, pooled SD = 22, alpha error = .05, power of the test = .9, the sample size determined for each grouis 12, or 24 subjects total. In consideration is a possible 10% loss calculation, a total maximum number of up 26 subjects or up to a maximum of 13 subjects per group is determined.

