11.4 Level of significance and power

The level of significance, or alpha error selected is equal to .05, which is interpreted as the Type I error for acceptance of Alternative Hypothesis or H_1 , with 95% confidence. The power

of the test, is set at .9, which is interpreted as the Type II error (beta), rendering an error of .1 or 10% for incorrect acceptance of the Null Hypothesis or H_0 .

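### The primary closure-time comparison is a valid but unadjusted t-test, although laceration length and location are recorded before randomisation; a prespecified ANCOVA would probably be more precise at little cost

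*Protocol*

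**What the plan says.** Section 8.3 sets a two-sided hypothesis on mean procedure time, with the null "Mean time for Zip 4 device wound closure procedure = Mean time for standard of care sutures wound closure procedure". Section 11.1 names the test: "Students 't' Test for comparative testing, will address testing the hypothesis statements". Baseline characteristics are only to be described by arm. The synopsis gives the same test and names no covariate either.

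The Visit 1 list in section 9.8.1.1 includes "Physical examination of the laceration (type, size, location") and places it ahead of randomisation. The CRF follows the same order: laceration length, body area and whether the wound lies on a bending part come on pages before the randomisation page. Randomisation is in blocks at 1:1, and no stratification factor is given.

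Section 9.6.3 derives 24 subjects, or up to 26 with dropout, and then adds: "Since different areas of the body are being appreciated we will enroll 60 patients". The synopsis and section 9.1 say 30 subjects, and section 11.2 allows at most 26.

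**The concern.** Longer wounds, or wounds at awkward sites, may plausibly take longer to close under either method. If so, an unadjusted comparison counts that variation as noise. With 13, 15 or 30 subjects per arm and no stratification, one arm can by chance receive longer wounds, and the observed time difference moves with that imbalance.

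The primary objective is to evaluate time and cost savings, and section 8.4 ties the time reduction to a cost claim. The width of the interval around the time difference therefore matters as well as the p-value. The variables needed to narrow it are already collected, and the analysis does not use them.

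**Working it through.** **Inputs from the protocol.** Section 11.2: "delta difference of 30 mins, pooled SD = 22", power 0.9. Section 11.4: "The level of significance, or alpha error selected is equal to .05". Section 8.3: two-sided. Arm sizes: 13 (section 11.2 maximum), 15 (total of 30) or 30 (total of 60).

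**Inputs assumed.** R², the share of closure-time variance explained by the covariates, is not in the protocol; the range used is 0.1 to 0.4. A true difference of 15 min is used once below and is also not a protocol figure.

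**1. Reproduce the plan's own figure.** n per arm = 2(1.960 + 1.282)² × 22² / 30² = 11.3, so 12 per arm and 24 in total, as stated. The calculation makes no allowance for covariates and so matches the unadjusted test.

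**2. Unadjusted power at 30 min, SD 22 (noncentral t).** 91.5% at 13 per arm, 95.0% at 15 and 99.9% at 30.

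**3. Interval width with adjustment.** Multiplying the unadjusted half-width by √(1−R²) alone is too optimistic. It leaves out the degrees of freedom spent and the variance cost of chance covariate imbalance. For k normally distributed covariate terms, the mean half-width is approximately

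t(0.975, 2n−2−k) × 22 × √(1−R²) × √(2/n) × √(1 + k/(2n−k−3)) × (1 − 1/(4·df)),

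where df = 2n−2−k and the last factor converts to the mean of the estimated SD.

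Example, n = 15, k = 1, R² = 0.1: 2.052 × 20.87 × 0.365 × 1.019 × 0.991 = 15.8 min.

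Example, n = 15, k = 3, R² = 0.1: 2.060 × 20.87 × 0.365 × 1.061 × 0.990 = 16.5 min.

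Simulation of the linear model agrees. Mean 95% CI half-width in minutes:

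| Per arm | Unadjusted | One covariate df, R² 0.1 to 0.4 | Three covariate df, R² 0.1 to 0.4 |
|---|---|---|---|
| 15 | 16.3 | 15.8 to 12.9 | 16.5 to 13.4 |
| 30 | 11.3 | 10.8 to 8.9 | 11.0 to 9.0 |

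At 13 per arm with three covariate df and R² = 0.1, the half-width goes from 17.6 to 18.0, slightly worse than unadjusted.

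**4. If R² is zero.** The same formula with one covariate gives 2.052 × 22 × 0.365 × 1.019 × 0.991 = 16.6 at 15 per arm (against 16.3), and 2.002 × 22 × 0.258 × 1.009 × 0.996 = 11.4 at 30 per arm (against 11.3). This is the price of a useless covariate.

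**5. Chance imbalance.** The SD of the shift in the unadjusted difference due to the covariates is 22 × √R² × √(2/n). That is 1.8 to 3.6 min at 30 per arm and 2.5 to 5.1 min at 15 per arm. It is already part of the unadjusted standard error and does not come on top of it.

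**6. Power.** If the true difference were 15 min, power at 30 per arm would rise from about 74% to 76–91% across one to three covariate df. At 15 per arm with three df it would go from 44% to 43% at R² = 0.1 and 59% at R² = 0.4. At the protocol's 30 min, the gain cannot exceed 5 percentage points at 15 per arm (from 95.0%) or 0.1 at 30 per arm (from 99.9%).

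**The case against.** The strongest reply is that nothing here is wrong. The t-test is unbiased under randomisation, controls type I error and matches the sample-size calculation. Power at the planned difference is already high. That stands, and it is why the point concerns efficiency. A reader might infer that omitting wound length biases the comparison or invalidates the p-value; the randomised design does not support that.

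A second reply is that covariates may be set in a statistical analysis plan that is not shown. That carries some weight, but the protocol has itself fixed the primary test in section 11.1 and the synopsis.

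A third is that the prognostic strength of length and site is not documented. This is correct. Timing runs from wound preparation to dressing, parts of which need not scale with length, and eligibility is limited to simple, straight, low-tension wounds up to 4 cm. A reader might take section 9.6.3 as an admission that body area drives closure time. The sentence does not mention closure time and cannot carry that reading.

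A fourth is that adjustment is not free in a very small trial. This also stands: with three covariate df and 13 or 15 per arm, there is no gain at R² = 0.1.

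**Conclusion.** The point holds as a cheap improvement. Section 11.1 leaves recorded pre-randomisation information out of the primary analysis. At 30 per arm, adjustment for one covariate would narrow the mean interval half-width by about 0.5 to 2.4 min (11.3 to 10.8–8.9) for R² of 0.1 to 0.4. At 15 per arm it would narrow it by about 0.5 to 3.4 min (16.3 to 15.8–12.9). The benefit lies in the precision of the estimate and in protection if the true difference is smaller than planned; at 30 minutes the power gain is small at 15 per arm and negligible at 30.

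These sizes rest on SD 22, on the assumed R² range and on normal covariates. If R² is near zero, precision falls slightly. A reader might conclude that adding every recorded wound feature would be better still; at 26 or 30 subjects the figures do not support that.

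**What to change.** In section 11.1 and the synopsis, make the primary analysis a linear model (ANCOVA) of procedure time on randomised arm and laceration length as a continuous covariate. Add one coarse body-area indicator only if the reconciled total is 60. The many location boxes on the CRF are too fine to enter as they stand, so define the grouping in advance, once it is settled whether the face is eligible (the synopsis includes it, section 9.6.1 does not). Report the adjusted mean difference with its 95% CI and keep the Student t-test as a supportive analysis.

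Fix the covariates before any closure times are examined. The trial is open-label and section 11.6 foresees testing closure times at an interim look, so a later choice could appear data-driven.

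Cost: a sentence or two of text, no new data and no extra subjects; one or two degrees of freedom for the model proposed here, and a slight loss of precision if length and site turn out not to matter. The total sample size (26, 30 or 60) has to be reconciled first, because it decides how many covariates the model can carry.

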11.2 Sample size

Sample sizes for the two treatment groups of Zip 4 device and SoC suture, were determined, and based on prior studies performed for the primary endpoint of mean times for incision closure time. The justification for sample sizes determined, is based on the following delta differences, and pooled Standard Deviation (SD) calculations for mean time differences of closure methods.

Differences and variances are based on prior data, with a delta difference of 30 mins, pooled SD = 22, alpha error = .05, power of the test = .9, the sample size determined for each grouis 12, or 24 subjects total. In consideration is a possible 10% loss calculation, a total maximum number of up 26 subjects or up to a maximum of 13 subjects per group is determined.

11.3 Data Sets to be analyzed

- a. Safety data will include all relevant safety data from consenting subjects in this investigation.
- b. The Full Analysis Set (FAS) will include randomization (random order) of participant subjects in the study.
- c. The Per Protocol Set (PPS) will include the following:
 - I. Randomization applied to participating subjects
 - II. Completion of PPS to the study endpoint objectives in accordance with this Protocol. This to be performed without any significant protocol deviations, which could have potential erroneous affect on the studies' efficacy, e.g. protocol violation could be a change to specific criteria per the primary and secondary endpoints.

The final criteria specified per the PPS, regarding protocol deviations, if any, that warrant exclusion, will be determined at the time of the database "lock meeting," when all data on any protocol violations or deviations are revealed.

11.4 Level of significance and power

The level of significance, or alpha error selected is equal to .05, which is interpreted as the Type I error for acceptance of Alternative Hypothesis or H_1 , with 95% confidence. The power

of the test, is set at .9, which is interpreted as the Type II error (beta), rendering an error of .1 or 10% for incorrect acceptance of the Null Hypothesis or H_0 .

11.5 Drop-out rates

The drop-out rate or "Loss" is based on a 10% loss (L) estimate for this study. Loss calculation = (sample n/(1-L).

11.6 Interim analysis

At the 10 day interview and data gathering point, an Interim Analysis will provide any meaningful subject feedback or inputs to VAS scores. Additionally, closure time data will be available at that time, for an initial analysis of the Primary Endpoint with mean, standard deviation, and "t" significance testing of the Hypotheses.

11.7 Criteria for termination on statistical grounds

The criteria applicable for termination is based only if an incomplete study subject sample size taken from the population, i.e. not meeting the sample sizes (n) specified for this study, or if the randomization methodology (order) is not adhered to during the administration of the investigation.

11.8 Reporting of deviations from the original Statistical Analysis Plan

Any deviation discovered throughout the study from the original Statistical Analysis Plan (SAP), will be described with justification in a CIP Amendment to the final report, as deemed appropriate.

11.9 Missing, unused or spurious data

Spurious data, also known as outliers or mavericks, will be included in the summary tables, though noted in study as abnormal data. Premature withdrawn subject data will also be inclusive to the analysis, as far into the study as possible. Any missing data discovered will be incorporated to the analysis, and noted accordingly.

11.10 Exclusion of particular information from the testing of the hypothesis

Since the primary endpoint and the testing of the hypothesis is based specifically on mean closure times, there may be exclusion of extraneous data or information not related to the hypotheses being tested, if applicable.

12 DATA MANAGEMENT

Data management will be conducted in accordance with applicable guidelines. A study specific Data Management Plan (DMP) will describe in detail the management of all subject data collected in the study. Any deviations, i.e. discrepancies and additions from the procedures defined in the DMP, will be described in a study specific Data Management Report (DMR).

All subject data will be collected in designated paper CRF and questionnaires. The PI or an authorized person will record subject data in the CRF in a precise and accurate manner. Abbreviations should not be used. The PI is responsible for the data entered and sign off the CRF at the end of the clinical investigation. The data should be recorded as soon as they are generated.

The subject data will be entered into a designated MS SQL database on a secure PFT. The database will be designed for the sole purpose of compiling and handling data from the ZipLine Study. The ZipLine database will be validated prior to study data entry. Responsible data management personnel will receive training and login credentials. Single data entry type will be applied.

Data validation/data cleaning procedures will be performed to assure validity and accuracy of the clinical data. These procedures consist of manual reviewing during data entry, as well as computerized edit checks. For all detected errors, queries will be raised to site for identifying out-of-range data values, CIP deviations, incomplete or inconsistent data.

Upon completion of the Zipline study, all study data will be verified from the original CRFs/ questionnaires and a complete data quality control of the database will be performed. After all discrepancies are resolved and the reconciliation with the SAE database is done, the database will be locked and the data will be analyzed.

12.1 Data Retention

The medical file of clinical investigation subjects must be retained in accordance with local legislation and in accordance with the maximum period permitted by the hospital, institution or private practice.

The Investigator shall retain all clinical investigation records during the investigation and for the period required by the applicable regulatory requirements or for at least 10 years after the premature termination or completion of clinical investigation, whichever is the longer. The PI must take measures to prevent accidental or premature destruction of these documents. The Investigator should contact the Sponsor prior to destruction of any records or reports pertaining to the clinical investigation to ensure they no longer need to be retained. In addition, if the PI leaves the hospital, he/she should provide the Sponsor with the name and address of the person who will look after and be responsible for the clinical investigation-related records. If the records will be transferred to another person/party, the transfer will be documented at the investigation site or at the Sponsor.

13 AMENDMENTS TO THE CIP

Any change to the approved clinical investigation documents will be documented and include a written justification. Any effects of the implemented changes on other clinical investigation documents shall be evaluated and documented. If deemed necessary, affected documents shall be properly updated and relevant parties notified. The version number and date of amendments shall be documented.

Proposed amendments to the CIP shall be agreed upon between he Sponsor and PI. The amendments shall be notified to, or approved by, the IEC.

All amendments to the CIP will be documented in an amendment log and communicated to relevant parties.

14 DEVIATIONS FROM THE CIP

A CIP deviation is a failure to follow, intentionally or unintentionally, the requirements of the CIP. Every effort should be made to comply with the requirements of the CIP and the Investigator is not allowed to deviate from the CIP.

As required by national regulations or guidelines, requests for deviations and reports of deviations will be provided to the IEC if the deviation affects subject's rights, safety and wellbeing, or the scientific integrity of the clinical investigation.

Under emergency circumstances deviations from the CIP may proceed without prior approval by the Sponsor and favorable opinion of the IEC if the rights, safety and well-being of the human subjects need to be protected. Such deviations will be documented and reported to the Sponsor and IEC as soon as possible in accordance with national regulations.

When the monitor or Sponsor identifies that the PI is out of compliance, this will be notified to the PI in writing, with a request to correct the source of the deviation immediately. Corrective action will be implemented to avoid repeated non-compliance, which will usually include re-training and may include terminating the clinical investigation at the site.

The Sponsor is responsible for analyzing deviations and assessing their significance. Corrective action will be implemented to avoid repeated deviations, which may include suspending the clinical investigation, disqualify the PI.

15 STATEMENTS OF COMPLIANCE

This clinical investigation will be conducted in accordance with the ethical principles that have their origin in the Declaration of Helsinki (*Appendix C*). Furthermore, the clinical investigation will be conducted in compliance with ISO 14155:2011 and applicable regional or national regulations.

15.1 Institutional Ethics Review

The final CIP, including the final version of the ICF, must be approved or given a favorable opinion in writing by an IEC before enrolment of any subject into the clinical investigation. The PI is responsible for informing the IEC of any amendment to the CIP as per local requirements.

Any additional requirements imposed by the IEC shall be followed.

15.2 Insurance

The Sponsor will be responsible for ensuring adequate insurance covering any injuries to the subject caused by the investigational medical device.

16 INFORMED CONSENT PROCESS

All subjects and legal authorized representatives will receive written and verbal information regarding the investigation beforehand. This will emphasize that participation is voluntary and that the subject may withdraw from the investigation at any time and for any reason. If new vital information appears during the clinical investigation the subject will be informed both orally and in writing. All subjects will have the opportunity to ask questions about the investigation and will be given sufficient time to decide whether to participate or not. Before any investigation-related procedures, the information consent will be signed and dated by the subject, their legal acceptable representative(s), and by the Investigator who gave the verbal and written information.

The only exception to the above is if not all legal representative(s) are present at the investigation site at the time for consent. The additional legal representative(s) will receive verbal information about the investigation through the phone, and will give their oral consent prior to any investigation-related procedures. Signed consent will be given as soon as possible thereafter.

The written subject information, PIS, explains that the data will be stored in a computer database, maintaining confidentiality in accordance with national data legislation, and that authorized representatives of the Sponsor, FDA, CA, and/or IEC may require direct access to those parts of the medical records relevant to the investigation, including medical history, for verification of data. Additionally, the written information specifies that data will be recorded, collected, processed and may be transferred (to either EEA countries and/or non-EEA countries). In accordance with the EU Data Protection Directive (95/46/EC), the data will not identify any subjects taking part in the investigation.

